3.7.2 Acute Physiology and Chronic Health Evaluation II (APACHE II)

APACHE II scores measure disease severity and will be obtained at screening. Exploratory stratified analyses will be based on APACHE II scores of greater than or equal to 10 vs. APACHE less than 10.

If there are missing data in the components comprising the APACHE II, then some factors may only be evaluable based on medical judgment. If this is the case, Sponsor will provide completed screening APACHE II scores for each randomized patient and the APACHE II scores will not be considered part of the audited clinical data set provided by the data management CRO.

3.8 Clinical Laboratory Assessments

Safety laboratory investigations will include results of hematology labs (CBC including platelets and white blood cell differential), and of blood chemistry labs (Glucose; Electrolytes (Sodium, Potassium, Chloride, Bicarbonate, Calcium, Phosphorus); Renal function tests (Urea/BUN, Serum Creatinine); Liver function tests (Albumin, Bilirubin Total, Alanine transaminase (ALT), Aspartate

transaminase (AST), Alkaline phosphatase (ALP); Total Protein). Also, urine albumin / creatine ratio will be evaluated.

Pregnancy testing will be done on all women of childbearing potential participating in the study (using the quicker of a blood test or urine test).

Clinical laboratory assessments will be collected at intervals according to time and events in Section 18.1 of the Clinical Trial Protocol.

Hematology will be collected at Screening, Day 1, Day 3, Day 7, Day 14, and Day 29.

Blood chemistry will be collected at Screening, Day 1 (bilirubin and creatinine only), Day 2 (creatinine only), Day 3 (bilirubin and creatinine only), Day 7, Day 10 (creatinine only), Day 14, Day 21 (creatinine only), Day 29 (albumin and creatinine only), 3 to 21 days after Day 29 visit (creatinine only), and at 3 months (creatinine only). The standard C-Reactive Protein (CRP) test (not the high sensitivity-hsCRP) will be used to evaluate inflammatory response and will be obtained at Screening and Days 7, 14, and 29.

Urine will be collected at Screening, Day 1, Day 3, Day 7, Day 14, Day 29 and Month 3 to measure albumin/creatinine ratio to evaluate renal function and potential injury.

3.9 Microbiology

Microbiological testing will be performed as described in the Clinical Study Protocol time and events schedule. Testing will be performed on blood specimens at Screening and intra-abdominal specimens from the first surgical or interventional radiology procedure, respectively.

3.10 Creatinine, AKI, AKD, and eGFR

3.10.1 Reference Creatinine

Exhibit 1 summarizes the algorithmic determination of reference creatinine. The algorithmic determination of baseline AKI stage will be based on comparing screening creatinine to the reference creatinine determined by Exhibit 1.

Note: If there is any discrepancy between the algorithm and the assignment by the site as to reference creatinine then this will generate a medical review which may result in a modified baseline AKI stage different from the algorithmic determination. All such cases will be documented in the clinical study report. Sensitivity analyses will be conducted as needed to evaluate the impact of any modifications from the algorithmic determination.

Exhibit 1. Algorithmic Determination of Reference Creatinine		

Preprocessing step: Creatinine values obtained within 2 days of dosing will be handled as follows: If there is only one value, this value will be excluded as input to the algorithm below. If there are more than one value, compare the maximum to the minimum, and if within 25%, then all values will be included as input to the algorithm below. If greater than 25%, then the values obtained within 2 days will be excluded as input to the algorithm below.
		

This table indicates the rules to be used to determine reference creatinine based on the numbers of historical values available during the last 3 months prior to screening and available 4 to 12 months prior to screening. In general, the algorithm prioritizes use of historical creatinine values obtained within the last 3 months.
		
Number of last 3 month values	Number of 4 to 12 months	Rule
0	0	Use MDRD to determine reference creatinine.
0	1	Use the 4- to 12-month value.
0	>=2	Use median of 4 to 12 month values.
1	0	Use <= 3-month value.
>=2	>=0	Use median of <= 3-month values.
1	1	Use the mean of the two available values.
1	>=2	Use the median of all available values.
>=2	1	Use the median of all available values.

The SAS code used to implement the MDRD formula^{1,2} to determine a reference creatinine when no historical values are available is:

```

if sex='Male' and black=0 then do;
  t1 = der_age**(-0.203) ;
  t2 = 1;
  t3 = 1;
  t4 = 186 * t1 *t2 *t3 ;
  Scrt = (75 / t4 )**(-0.887) ;
end;

if sex='Female' and black=0 then do;
  t1 = der_age**(-0.203) ;
  t2 = 0.742;
  t3 = 1;
  t4 = 186 * t1 *t2 *t3 ;
  Scrt = (75 / t4 )**(-0.887) ;

```

¹ Levey AS, Bosch JP, Lewis JB, Greene T, Rogers N, Roth D; Modification of Diet in Renal Disease Study Group. A more accurate method to estimate glomerular filtration rate from serum creatinine: a new prediction equation. Ann Intern Med 1999 Mar;130(6):461-470.

² Levey AS, Greene T, Kusek I, Beck G. A simplified equation to predict glomerular filtration from serum creatinine (Abstract). J Am Soc Nephrol 2000;11:155A]

```
end;

if sex='Male' and black=1 then do;
  t1 = der_age**(-0.203) ;
  t2 = 1;
  t3 = 1.21;
  t4 = 186 * t1 *t2 *t3 ;
  Scrt = (75 / t4 )**(-0.887) ;
end;

if sex='Female' and black=1 then do;
  t1 = der_age**(-0.203) ;
  t2 = 0.742;
  t3 = 1.21;
  t4 = 186 * t1 *t2 *t3 ;
  Scrt = (75 / t4 )**(-0.887) ;
end;
```

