 5. Initial diagnosis of AKI established either upon presentation to medical care at the study site in those patients with suspected or confirmed abdominal infection or surgically confirmed NSTI; or in those patients in whom the initial diagnosis of AKI is established during the 48-hour period from the suspected or confirmed diagnosis of abdominal infection or surgical confirmation of NSTI.

AKI Stage 2 or 3 according to the following KDIGO AKI criteria:

a. Stage 2 AKI

- i. Increase in serum creatinine to $\geq 200\%$ (≥ 2.0 -fold) from a reference creatinine value (see below) in the absence of primary underlying renal disease (eGFR >30 mL/min)

OR

- ii. Urine output < 0.5 mL/kg/hr x 12 hours following adequate fluid resuscitation [the aggregate over any 12-hour period can be used with hourly rate being relatively persistent over the 12-hour period]

Urine output should be calculated using Ideal Body Weight (IBW; using the Miller Formula⁵²)

b. Stage 3 AKI

- i. Increase in serum creatinine to $\geq 300\%$ (≥ 3.0 -fold) from a reference creatinine value in the absence of primary underlying renal disease (eGFR >30 mL/min)

OR

- ii. Serum creatinine ≥ 4 mg/dL

OR

- iii. Planned or initiation of RRT for acute AKI

- Order for RRT must be in place
- RRT may be started prior to study drug administration as long as the patient is off RRT during study drug administration and up to at least one hour post study drug administration

OR

- iv. Urine output < 0.3 mL/kg/hr x 24 hours or anuria x 12 hours following adequate fluid resuscitation
 - Urine output should be calculated using IBW (using the Miller Formula)

The reference creatinine value is the serum creatinine value according to the following order:

- i. Value within 3 months of the hospital admission
 - If single value available, then use the single value for reference
 - If two values available, then use the average of two values for reference
 - If three or more values available, then use the median of the three most recent values for reference
 - ii. Value between 3 and 12 months prior to hospital admission
 - If single value available, then use the single value for reference
 - If two values available, then use the average of two values for reference
 - If three or more values available, then use the median of the three most recent values for reference
 - iii. At hospital admission (if the patient is admitted without an acute illness)

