7.3 Schedule of Procedures/Visits

A schedule of study assessments is shown in Section 18-Appendix A (“Study Visits and Procedures”) of the protocol. Homecare services will be offered through a third party vendor (i.e., Symphony Clinical Research) using trained, qualified homecare professionals. Provision of this service is intended to help ensure patient retention and data collection when travel to the clinical trial sites may be overly burdensome for the participants given their disease state. Symphony Clinical Research is contracted to evaluate subjects as outpatients from Day 7 through Day 90.

Local laboratories will be used during hospitalization and clinic visits while the home health service will send samples to a central laboratory. Outpatient samples may be evaluated by other local laboratories if acceptable accreditation.

Patients who are registered and randomized for the study, but do not receive study drug (part of the Intent-to-Treat (ITT) population) should continue to be followed through Day 90 with as much data collected as part of SOC entered into the eCRF. No additional procedures or laboratory studies should be performed beyond SOC as part of the research study. The entered data will match as closely as possible the SoC assessments and laboratory evaluations with the visit days.

Visit 1: Screening

Evaluation starts once a patient presents with clinical diagnosis of abdominal infection.

- Obtain ICF
- Verification of Inclusion/Exclusion criteria
- Demographics, medical history, infection history, concomitant medications, vital signs, height, weight, physical exam (PE). Race is not entered for European countries.
- Record urine output from presentation or around (before) time of diagnosis of abdominal infection or NSTI recorded to study drug administration or until 48 hour window to develop Stage 2 or 3 AKI ends
- Record serum creatinine values every 6 hours from presentation or around (before) time of diagnosis of abdominal infection until study drug administration or until 48 hour window to develop Stage 2 or 3 AKI ends (blood draws may be adjusted to when blood is normally collected on the unit)
- Determine kidney size by CT or renal ultrasound if patient does not have a reference creatinine value within the past 12 months
- Recording baseline signs and symptoms and AEs/SAEs (AEs of Screening are AEs/SAEs starting after obtaining ICF until study drug administration)
- Safety baseline laboratory tests:

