3.10.2 Screening AKI and Screening eGFR

Screening (pre-dose) AKI will be determined by comparing screening (pre-dose) creatinine to the algorithmic determination of reference as described in Exhibit 1 based on the rules summarized in Exhibit 2.

The screening creatinine is necessary to establish baseline eGFR. However, according to the Clinical Protocol, the AKI stage used to determine eligibility into the study may be determined through urine outcome criteria. If there is any discrepancy between the algorithm and the assignment by the site as to reference creatinine then this will generate a medical review which may result in a modified baseline AKI stage different from the algorithmic determination. However, in all cases, the algorithmic determination will be used when determining eGFR. All such cases will be documented in the clinical study report. Sensitivity analyses will be conducted as needed to evaluate the impact of any modifications from the algorithmic determination in Screening AKI stage.

Exhibit 2. Algorithmic Determination of Screening (pre dose) AKI Stage	
Stage	Serum Creatinine
0	<1.5 times reference
1	1.5 to <2.0 times reference
2	≥2 to 3 times reference
3	≥ 3 times reference OR Increase in serum creatinine to ≥4 mg/dL OR Initiation of renal replacement therapy
Reference may be either algorithmically determined or independently adjudicated depending on analysis.	

Screening eGFR will be determined using the following formula.

$$\text{Screening eGFR (mL/min/1.73 m}^2\text{)} = 175 \times (\text{Screening Cr})^{-1.154} \times (\text{Age})^{-0.203} \times (0.742 \text{ if female}) \times (1.212 \text{ if African American}).$$

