3.10.6 Additional Processing Details

Based on experience gained through processing of AKI endpoints in the recently completed ATB-202 study, the following data processing convention will be employed.

- To account for renal replacement therapy (RRT), the exact dates on which the patient is on dialysis will be determined and compared to the exact date on which the labs were drawn for the creatinine sample. If the sample was drawn within 2 days from RRT start then it was excluded from all analyses.
- If the reference creatinine is greater than 1.4, then all available creatinine values obtained on Day 10 and after, including unscheduled visits, will be evaluated. If the maximum is 1.5x the minimum, then the reference creatinine is replaced by the MDRD.
- LOCF will be used for missing Day 14 creatinine starting from Day 10.
- LOCF will be used for missing Day 28 creatinine starting from Day 7.

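### SAP Exhibit 1 can make an AKI-level creatinine the reference value, so that a flat, unrecovered patient passes the primary endpoint's eGFR criterion

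*SAP*

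**What the plan says.** **Reference creatinine (SAP 3.10.1, Exhibit 1).** Values drawn within 2 days of dosing are handled first.

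- One value: "If there is only one value, this value will be excluded as input to the algorithm below".
- More than one: "compare the maximum to the minimum, and if within 25%, then all values will be included as input to the algorithm below".
- Wider spread: "If greater than 25%, then the values obtained within 2 days will be excluded as input to the algorithm below".

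The surviving values go into a table indexed by the number of values in the last 3 months and at 4 to 12 months. With two or more recent values the rule is "Use median of <= 3-month values". With none in either period, the reference is back-calculated by MDRD at 75 mL/min.

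**Protocol 6.1.** The reference is taken from values within 3 months, then from 3 to 12 months, and last "At hospital admission (if the patient is admitted without an acute illness". SAP section 1 states that the SAP prevails over the protocol where they differ.

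**Sampling.** The screening visit in protocol 7.3 asks sites to "Record serum creatinine values every 6 hours from presentation or around (before) time of diagnosis of abdominal infection until study drug administration".

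**Endpoint.** SAP 2.1.1 and 4.1 require being alive, free of dialysis and below a 37% loss from the patient's reference eGFR at Day 28. The formulas in 3.10.3 to 3.10.5 compute the loss from screening eGFR instead.

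**Possible safeguards.** A site-versus-algorithm discrepancy triggers a medical review, which may change baseline AKI stage, but "in all cases, the algorithmic determination will be used when determining eGFR" (3.10.2). Under 3.10.6, if the reference exceeds 1.4, creatinines from Day 10 on are examined: "If the maximum is 1.5x the minimum, then the reference creatinine is replaced by the MDRD".

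**The concern.** Agreement within 25% shows that creatinine is stable, not that it is normal. A patient who arrives with established AKI and has two similar values before dosing satisfies the rule. Those values can then set the level from which loss is measured, where the protocol intends a pre-illness level. A patient whose kidneys never recover is scored as having lost nothing.

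Such false successes can occur in both arms. If they are equally likely among eGFR failures in each arm, both success rates rise, the difference shrinks and power falls.

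The window is also described only as within 2 days of dosing, without saying before or after. Protocol 7.3 schedules creatinine on Days 1, 2 and 3, so a literal reading could let post-dose values into the reference.

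**Working it through.** **1. The plan's own power figure.** SAP 2.1.2: 60 per arm, 75% vs 50%, one-sided 0.05. With the pooled-variance normal approximation,

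power = Φ{[d − z·√(2p̄(1−p̄)/n)] / √([p₁(1−p₁)+p₀(1−p₀)]/n)}

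= Φ{[0.25 − 1.645 × 0.0884] / 0.0854} = 0.890. This matches the SAP's 89%. At one-sided 0.025 the same formula gives 0.816, matching protocol 12.5.2.

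**2. The creatinine ratio behind a 37% loss.** The MDRD exponent is −1.154 (SAP 3.10.3). Age, sex and race cancel, so loss = 1 − (Cr Day 28 / Cr reference)^−1.154. A 37% loss corresponds to a ratio of 0.63^(−1/1.154) = 1.492.

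**3. Worked example** (illustrative values: pre-illness 1.0 mg/dL; in-window 2.4 and 2.5; Day 28 creatinine 2.4).

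- Agreement: 2.5/2.4 = 1.04, so both values are admitted.
- One historical value: median of 1.0, 2.4, 2.5 = 2.4.
- Loss under the rule: 1 − (2.4/2.4)^−1.154 = 0%, success.
- Loss from 1.0: 1 − 2.4^−1.154 = 63.6%, failure.
- Highest passing Day 28 creatinine: 2.4 × 1.492 = 3.58.

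**4. Dependence on the number of historical values** (each 1.0, within 3 months, none at 4 to 12 months).

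| Historical values | Reference | Loss at Day 28 = 2.4 | Result |
|---|---|---|---|
| 0 | 2.45 | −2.4% | pass |
| 1 | 2.4 | 0% | pass |
| 2 | (1.0+2.4)/2 = 1.7 | 32.8% | pass |
| 3 | 1.0 | 63.6% | fail |

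At equal counts the median falls midway and the result depends on the AKI level. With in-window 3.0 and 3.2, two historical values of 1.0 and Day 28 at 3.0, the reference is 2.0 and the loss 37.4%, a narrow failure. With four in-window values from 3.0 to 3.3, the patient passes with up to three historical values. Two table rows overlap (two or more recent values with exactly one older value), and the choice of row can also flip a borderline case.

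**5. Cases the rule handles correctly.** A single in-window value is excluded, as is a rising series such as 1.6, 2.2, 3.0. Both patients then fail at Day 28 = 3.0: loss is 71.9% from a historical 1.0, or 69.5% from the MDRD reference of 1.07 (man aged 60, not Black).

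**6. The 3.10.6 override** (reference 3.1 from in-window 3.0 and 3.2; true baseline 1.0).

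| Creatinine from Day 10 on | Max/min | Override | Scored loss | True loss |
|---|---|---|---|---|
| 2.9 to 3.0, flat | 1.03 | no | −3.9%, pass | 71.9% |
| 3.0 falling to 2.1 | 1.43 | no | −56.7%, pass | 57.5% |
| 3.0 falling to 1.9 | 1.58 | yes, reference 1.07 | 48.4%, fail | 52.3% |

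The override responds to change, so it misses the flat patient.

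**7. Illustrative power at one-sided 0.05.** Assume true rates of 75% and 50%, of which 8 and 20 points of failure are due to eGFR alone, and a share m of those failures turned into successes. The rates become 75+8m and 50+20m.

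| m | Rates | Difference | Power |
|---|---|---|---|
| 0 | 75 / 50 | 25 | 89% |
| 25% | 77 / 55 | 22 | 82% |
| 50% | 79 / 60 | 19 | 74% |
| 75% | 81 / 65 | 16 | 63% |

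**The case against.** **The formula in 3.10.3 does not use the reference.** It computes loss from screening eGFR. In the example, with screening 2.5 and Day 28 at 2.4, loss is 1 − (2.4/2.5)^−1.154 = −4.8%, a pass whatever Exhibit 1 returns. This stands. Exhibit 1 decides the endpoint only under the definition in 2.1.1 and 4.1, and correcting Exhibit 1 alone could change nothing. It does not clear Exhibit 1: once the formula is brought into line with the definition, the reference rule determines success.

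**How common it is.** A reader might infer that two concordant AKI values are the usual picture in patients presenting with AKI. The documents do not support that. Protocol 7.3 and Appendix A specifically call for 6-hourly repeats in patients without AKI at presentation, and a later two-fold rise inside the window breaks the 25% limit. Patients with AKI at presentation are to be dosed within 6 hours and may have only one value. In an assumed one-compartment model (42 L, baseline GFR 100 mL/min) at 30% of normal GFR, two draws starting at twice baseline differ by 15% and are admitted. Adding one draw 6 hours earlier gives 1.61 to 2.30, or 43%, and all are excluded.

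**How in-window values are counted.** The table counts historical values before screening, so treating screening draws as last-3-month values is an interpretation. It is the natural one, because the text sends them into that table and no other column fits.

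**Analysis sets.** A reader might also infer that these patients drop out of the mITT set or the stage subgroups as algorithmic Stage 0. That does not follow. The discrepancy with the site's reference triggers a review that can restore the stage, the mITT definition asks for a definitive diagnosis, and Exhibit 2 assigns Stage 3 at 4 mg/dL or RRT whatever the reference.

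**Excluding every in-window value goes too far.** Patients may qualify on urine output alone. For them a stable creatinine below the AKI threshold may be a better baseline than an MDRD value. This stands and shapes the fix.

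**Conclusion.** The rule is wrong as written. It admits illness values that protocol 6.1 would not accept, and it can reverse a patient's primary-endpoint result. The conditions are specific: at least two in-window values within 25% of each other at AKI level, fewer historical values from the last 3 months than in-window values (at equal counts the result can go either way), and a patient alive and off dialysis at Day 28. Deaths and patients on dialysis still fail. The conclusion also assumes that loss is measured from reference eGFR, as 2.1.1 and 4.1 define it.

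For an affected patient the error is large: 0% instead of 64% in the example. For the trial, its size is unknown. The power figures rest on assumed shares that appear nowhere in the documents and should not be read as an estimate. With equal shares in both arms the effect is dilution; this calculation shows no inflation of the type 1 error.

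**What to change.** Before unblinding:

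1. **Exhibit 1 preprocessing.** Let creatinines from the 2 days before dosing enter the reference only if they do not meet creatinine AKI criteria against the historical reference, or against the MDRD value if there is none, or if they are the protocol's admission value in a patient admitted without acute illness. Exclude all post-dose values. Otherwise apply the remaining Exhibit 1 rows, including the MDRD row when no value is left, and resolve the overlapping rows. In the example the reference returns to 1.0 and the patient fails at 63.6%.
2. **Loss formulas in 3.10.3 to 3.10.5.** Replace screening eGFR with reference eGFR. Align the sentence in 2.1.1 and 4.1 that describes the loss as comparing screening eGFR with the reference creatinine. Without this step, step 1 may not reach the endpoint.
3. **Sensitivity analysis.** Report the current rule, with the number of patients whose Day 28 result changes.

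The cost is a short SAP amendment and some reprogramming, with no new data. The downside is that some more patients will have an MDRD-imputed reference, which assumes 75 mL/min.

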3.10.3 Day 28 eGFR

Day 28 eGFR will be determined by converting Day 28 creatinine to Day 28 eGFR using the following formula:

$$\text{Day 28 eGFR (mL/min/1.73 m}^2\text{)} = 175 \times (\text{Cr Day 28})^{-1.154} \times (\text{Age})^{-0.203} \times (0.742 \text{ if female}) \times (1.212 \text{ if African American}).$$

Percentage loss in eGFR at Day 28 will be determined using the following formula.

$$\text{Percentage loss in eGFR at Day 28} = 100\% \text{ times } [\text{Screening eGFR} - (\text{Day 28 eGFR}) / \text{Screening eGFR}]. \text{ If percentage loss } \geq 37\% \text{ then patient fails key secondary endpoint.}$$

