4.1 Primary Effectiveness Endpoint

The primary effectiveness endpoint is *freedom from durable loss of renal function at Day 28*. The primary effectiveness endpoint requires:

- (i) Alive at Day 28,
- (ii) Free of dialysis at Day 28, and
- (iii) Less than a 37% loss of estimated Glomerular Filtration Rate (eGFR; measured with the Modification of Diet in Renal Disease (MDRD) formula from the patient's reference eGFR) at Day 28.

Reference creatinine values, baseline AKI stage and percentage loss of eGFR at 28 will be determined through algorithmic determination (see details above). Percentage loss of eGFR determined algorithmically will be based on a comparison of eGFR at screening compared to an algorithmically determined reference creatinine value.

Note: The Clinical Protocol allows subjects to qualify for enrollment in terms of AKI stage through urine outcome.

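### The fallback reference creatinine and the eGFR formulas use two MDRD versions that are not inverses of each other, so an assumed reference eGFR of 75 comes back as 69.8–71.1

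*SAP*

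**What the plan says.** **Back-calculation.** When there is no historical value, Exhibit 1 in SAP 3.10.1 instructs: "Use MDRD to determine reference creatinine". The SAS code forms t4 = 186 × age^−0.203 × 0.742 (if female) × 1.21 (if black) and then computes "Scrt = (75 / t4 )(-0.887", that is, 75/t4 raised to the power −0.887. SAP 3.10.6 adds a second route. If a reference above 1.4 meets a variability condition from Day 10 on, "then the reference creatinine is replaced by the MDRD".

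**Forward conversion.** SAP 3.10.3 states: "Day 28 eGFR will be determined by converting Day 28 creatinine to Day 28 eGFR using the following formula". The formula is 175 × Cr^−1.154 × age^−0.203 × 0.742 (if female) × 1.212 (if African American). SAP 3.10.2, 3.10.4 and 3.10.5 use the same constants for Screening, Day 14 and Day 90. The Day 90 formula in 3.10.5, however, names the Day 14 creatinine as its input.

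**Use.** SAP 4.1 requires "Less than a 37% loss of estimated Glomerular Filtration Rate" from the patient's reference eGFR. SAP 3.10.2 says that the algorithmic reference is always the one used for eGFR. The same reference creatinine sets the algorithmic AKI stage in Exhibit 2. The SAP prints no separate formula for reference eGFR and does not explain the two sets of constants.

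**The concern.** A back-calculation is meant to undo the forward formula. Here the leading constant, the race factor and the exponent all differ, so a patient assigned an eGFR of 75 no longer has 75 once the derived creatinine is converted with the SAP's own equation.

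Three things depend on this:

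- what the 37% threshold means for patients whose reference is imputed;
- their algorithmic AKI stage, since the mITT definition in SAP 2.3 requires Stage 2 or 3;
- the reproducibility of the primary endpoint, because two programmers could convert the reference differently.

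The Day 90 input is a separate slip in the same set of equations. Coded as printed, the Day 90 endpoint would repeat the Day 14 kidney function.

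**Working it through.** **Inputs.** Back-calculation (SAP 3.10.1): target 75; constants 186, 1.21, −0.887. Forward formula (SAP 3.10.2 to 3.10.5): 175, 1.212, −1.154. The age term and the female factor 0.742 are the same in both. Threshold: 37%. Age range: 18 to 85 (protocol 6.1).

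**Step 1: is the exponent an inverse?** The exact inverse of −1.154 is −1/1.154 = −0.8666. The code's −0.887 inverts neither version.

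**Step 2: try to recover the plan's 75.** Take a non-black man aged 60.

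- 60^−0.203 = 0.4355, so t4 = 186 × 0.4355 = 81.01.
- Code creatinine = (75/81.01)^−0.887 = 1.0708 mg/dL.
- Forward: 175 × 1.0708^−1.154 × 0.4355 = 70.44, not 75.
- The exact inverse on the 175 scale is 1.0141 mg/dL, which does return 75.00. The code's value is 5.6% higher.

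**Step 3: all ages 18 to 85.** Effective loss from 75 = 1 − 0.63 × (returned eGFR)/75.

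| Group | Returned eGFR | Loss from 75 at the 37% cut-off |
|---|---|---|
| Non-black men | 70.0–70.6 | 40.7–41.2% |
| Black men | 69.8–70.4 | 40.9–41.3% |
| Non-black women | 70.5–71.1 | 40.3–40.8% |
| Black women | 70.3–70.9 | 40.5–40.9% |

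The code's creatinine is 4.8% to 6.4% above the 175-consistent value. The Day 28 pass line lies at eGFR 44.0–44.8, against 0.63 × 75 = 47.25. A 37% loss equals a creatinine ratio of 0.63^(−1/1.154) = 1.492. For the man aged 60 the Day 28 limit is therefore 1.492 × 1.0708 = 1.60 mg/dL, against 1.492 × 1.0141 = 1.51 mg/dL.

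**Step 4: which mismatch matters?** The leading constant alone gives 75 × 175/186 = 70.56. The exponent alone gives 74.1–75.5. The race factor alone moves the result by about 0.1. The 186-versus-175 difference is nearly the whole effect.

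**Step 5: which scale do the documents point to?** Protocol Appendix F lists twice the normal creatinine in 24 age, race and sex cells. I computed the reference at mid-band age (last band taken as 66–85), rounded it to 0.1 and doubled it. The printed 186 code reproduces 23 of 24 cells and a 175-consistent version 11 of 24. Against an exact inverse on the 186 scale (186, 1.21, −1/1.154), the code's creatinine has a ratio of 0.994–1.011, so it agrees to about 1%.

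**Step 6: staging.** For a patient without a reference value, Appendix F admits a non-black man over 65 at 2.0 mg/dL. Twice the code's reference is 2.11 at age 66 and falls to 2.01 at age 85. A man admitted at 2.0 can therefore fall just short of algorithmic Stage 2, by at most about 0.1 mg/dL.

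**The case against.** **The 40–41% figure is conditional.** A reader might infer that patients with a 40–41% loss certainly pass. The documents do not establish that. SAP 3.10.3 prints Screening eGFR as the base of the percentage loss. Coded that way, the reference creatinine does not enter the Day 28 loss at all. If a programmer set the reference eGFR to 75 directly, the shift would also vanish. This objection stands, and the conflict between Screening and reference eGFR is a separate error that needs its own resolution.

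**The direction depends on the scale.** A reader might say that the fallback creatinine is too high. That assumes 175 is intended, and the documents do not say so. Appendix F, the entry rule for patients without a reference, fits the 186 scale much better. Harmonising on 186 would leave the creatinine pass line almost unchanged. This stands too, and it means the 175 constants should not simply be imposed on the back-calculation.

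**Different thresholds for two groups?** If every reference creatinine is converted with the 175 formula, every patient passes below 1.492 times his or her own reference, which is a 37% loss from it. What moves is the imputed reference relative to its stated 75.

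**Staging at 65.** A man aged exactly 65 falls in the Appendix F row with 2.2 mg/dL, above the code's 2.11, so he stays Stage 2. The effect starts at 66. A site–algorithm discrepancy in reference creatinine also triggers medical review of the baseline stage, although the eGFR calculation keeps the algorithmic value.

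**Day 90.** The sentence above the formula speaks of converting Day 90 creatinine, so the intent is clear and this is a copying slip. The printed formula is still wrong.

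None of this removes the inconsistency: no single MDRD version underlies both halves of the calculation.

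**Conclusion.** The inconsistency is real. For patients whose reference is set by MDRD, the printed code and the printed forward formula turn 75 into 69.8–71.1. On two assumptions, that loss is measured from reference eGFR and that the reference creatinine is converted with the 175 formula, the 37% cut-off becomes a 40.3–41.3% loss from the assumed 75.

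The practical size is limited. Only fallback patients are affected: those with no usable history and those moved to MDRD under SAP 3.10.6. The documents do not give their share. The staging effect is small and, in the case worked here, confined to non-black men aged 66 to 85 near the entry value. A reader might also infer a biased test, but the rule is identical in both arms. It changes who counts as a success and what the threshold means, not the type 1 error.

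The point should still be settled before unblinding, because a later change to the definition of success would be hard to defend as independent of the results.

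**What to change.** Before unblinding:

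1. Choose one MDRD version (leading constant and race factor) and use it in the back-calculation and in every eGFR formula, with the exact inverse exponent −1/1.154. Record the reason for the choice and check the resulting reference values against Appendix F.
2. Alternatively, set reference eGFR to 75 directly for fallback patients in the eGFR endpoint. With the 175 formulas kept, this puts the pass line at 47.25, so it is itself a choice of scale. AKI staging would still need a consistent reference creatinine.
3. State a formula for reference eGFR, and resolve separately whether Screening or reference eGFR is the base of the loss.
4. In SAP 3.10.5, make Day 90 creatinine the input to the Day 90 formula.

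The cost is a few lines of SAP text and code. For patients with a recorded reference, percentage loss from reference does not change, because the constants cancel. Among fallback patients the success rate may shift slightly: very little if 186 is adopted, and somewhat downward if 175 is.
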